In our literature review in The Lancet Oncology,[18] we looked at 85 manuscripts to determine whether historical literature has found a tangible association between presumed risk-increasing behavioral exposures (including ipsilateral skin puncture, cellulitis infections) and BCRL. We found that over the past several decades, the majority of published studies have demonstrated that the clinical benefit of current precautionary guidelines has not been established. Among 31 original studies examining the association between these exposures and BCRL, only eight are prospective cohort studies.[10,19,21–24] Among these, four studies demonstrate a significant correlation between lymphedema and commonly reported lifestyle-based risk factors, in one case, skin puncture.[24] The study that found a correlation between skin puncture and lymphedema was composed only of patients with ALND (n=188), and based on 8 patients who developed lymphedema after skin puncture.

In summary, skin puncture is not associated with increased arm volume based on available evidence.

COVID-19 Vaccine and Lymphedema Risk

Lymph node swelling is a known and common side effect of both the Moderna and Pfizer COVID-19 vaccines. This is the body's normal reaction to the vaccine. According to the Centers for Disease Control and Prevention, axillary swelling or tenderness (i.e., lymphadenopathy) was a solicited adverse event reported in 11.6% of patients (vs 5.0% for placebo) following dose 1 and 16.0% of patients (vs 4.3% for placebo) following dose 2 after the Moderna vaccine.[25] This occurred in the arm and neck 2-4 days following vaccination with a median duration of 1-2 days. After the PfizerBioNTech COVID-19 vaccine, lymphadenopathy was reported as an unsolicited adverse event with 58 more cases in the vaccine group than the placebo group (64 vs 6 respectively). This occurred in the arm and neck within 2-4 days of vaccination and lasted for a mean of 10 days.[26] Rates and duration of adenopathy in both trials were based on clinical assessment (i.e., physical examination). Anecdotally, mammographically detectable axillary adenopathy following COVID-19 vaccinations has been unilateral.[27]

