The invitation to participate was previously resent a second time after 72 hours with no response, and then a third time at seven days after initial contact (prior to new IRB regulations regarding reminders). An updated version of the recruitment letter was sent with the booster survey once this dose becomes available. The letter includes a new second survey link to questions about the booster vaccine. It is stated in the recruitment letter that this is an updated version of the study which makes the survey more user friendly and includes the booster dose. For this reason, all participants will receive the invitation to participate unless they have specifically asked not to be contacted about our study again. A follow up phone call may be made if we do not hear back in 2 weeks. For patients who do not complete the surveys after consenting to participate (either due to forgetting to finish the surveys or having technical difficulties finding the surveys), the Clinical Research Coordinator will call the participant at the phone number in the EPIC chart to assist in completing all surveys. A telephone script is attached.

Since booster doses of all vaccines are recommended by health officials at differing times, we will contact participants securely through Patient Gateway who have already completed survey(s) about their 1st/2nd doses asking them to complete the booster survey as well. This updated booster letter will include information regarding optional arm measurements as well. This states that we would like participants to make appointments for arm measurements 1-2 weeks before the booster, 7-14 days after the booster, 4-6 weeks after the booster, and 3 months after the booster, +/- 2 weeks. This is an optional component of participation in this study. The letter will be sent through patient gateway. The letter will be sent again to participants who have completed surveys about their 1st/2nd doses in March of 2022 as we anticipate many more responses now as the booster had become more widespread. Depending on response rates, we may reach out by phone, using the attached letter as a script, to help participants complete the booster survey.

98 participants are eligible for our study as well as the CANVAX: Cancer, COVID and Vaccination study (2021P000746). We have been collaborating with the CANVAX team and would like for as many participants as possible of these 98 to complete both studies. In the future, both teams will collaborate

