on how best to share our data (perhaps by applying for a data use agreement). Therefore, we will send an additional letter through Patient Gateway to these participants explaining why we would specifically appreciate their participation in the study, signed by the CANVAX PI. These participants have not opted out of being contacted for future research. The Lymphedema Research Program Clinical Research Coordinators are listed as Research Assistants on the CANVAX protocol. If a CANVAX patient is seen in the Breast Cancer Center for routine follow ups or arm measurements, CRCs will offer to have the patient fill out the survey during the visit. Depending on response rate from the Patient Gateway letter, CRCs may also call these patients (a script is attached) unless they decline to participate.

If the participant consents, they will immediately begin a survey asking for information about their first dose and symptoms and second dose and symptoms, if applicable. For participants who have had all doses of their respective vaccines, their participation is complete after responding to a survey about all applicable doses. For participants who have had one dose of their vaccine and plan to have a second, they will fill out the expected date of their second dose and told that the invitation will be resent on that date via Patient Gateway for them to fill out a second survey on that dose. A second link will be available in the recruitment letter directing participants to fill out experiences with the booster dose of the vaccine if they receive it. Copies of both surveys (first/second dose experience and booster dose experience) are attached.

[figure not shown]

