Additionally, we will reach out to participants through Patient Gateway who have consented to the study and experienced some form of swelling and provide them with contact information if they would like to schedule arm measurements before and/or after receiving the booster vaccination. All participants are aware that arm measurements remain available to them as they have in the past. Language for this letter is attached. We will resend an updated letter to participants who reported lymph node swelling after any of the three doses. The updated language is attached. As has been conducted with the booster arm measurements, parking will be compensated for those coming in for additional appointments outside of regular oncology visits. Depending on response rates, we may also reach out to participants by phone using the attached letter as a script.

An additional survey asking questions about prior SARS-CoV-2 infection will be sent to all participants who have consented to participate through answering questions on any doses of the vaccine. The CANVAX study recently published results that prior infection was associated with higher systemic, but not local, symptoms⁴³. We would like to test this in our population and therefore must collect data on any prior infections to

compare with the data we have on vaccine experiences. The invitation to complete this survey, attached, will be sent securely through patient gateway, and we may reach out by phone depending on response rates at the discretion of the PI. A consent addendum is included in the survey language, attached. No new subjects will be enrolled through this survey.

Participants will be aware (explained in consent fact sheet) that we may review their medical records for the purposes of this study and that we will analyze their survey data in conjunction with their breast cancer treatment information and lymphedema screening data.

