Given minimal risk to patients and the fact that it is an observational study, the main criteria for removing a subject from the study would be patient withdrawal from the study.

FORESEEABLE RISKS AND DISCOMFORTS

Provide a brief description of any foreseeable risks and discomforts to subjects. Include those related to drugs/devices/procedures being studied and/or administered/Performed solely for research purposes. In addition, include psychosocial risks, and risks related to privacy and confidentiality. When applicable, describe risks to a developing fetus or nursing infant.

Psychosocial risks may include frustration associated with receiving survey prompts as to whether the patient has received the first dose of the COVID19 vaccine, given this is an emotional topic currently. There could also be distress associated with the potential for the known side effect of lymph node swelling after receiving the COVID-19 vaccine in patients at risk for lymphedema.

EXPECTED BENEFITS

Describe both the expected benefits to individual subjects participating in the research and the importance of the knowledge that may reasonably be expected to result from the study. Provide a brief, realistic summary of potential benefits to subjects, for example, "It is hoped that the treatment will result in a partial reduction in tumor size in at least 25% of the enrolled subjects." Indicate how the results of the study will benefit future patients with the disease/condition being studied and/or society, e.g., through increased knowledge of human physiology or behavior, improved safety, or technological advances.

Benefits to society would include wide distribution of important patient education regarding the side effects and recommendations for safe receipt of the COVID-19 vaccine. This will minimize distress in our patients who experience a potentially alarming symptom such as lymph node swelling, which may concern patients who underwent lymph node removal. Since we

will be monitoring for symptoms, we will be able to direct patients to seek medical care in the event lymph node swelling symptoms persists to six weeks after the second dose. If there is clinical concern that persists ≥ 6 weeks after the final vaccine dose, axillary ultrasound is recommended per current MGH Breast Imaging standard of care. There are no direct benefits to patients who do not experience lymph node swelling.

EQUITABLE SELECTION OF SUBJECTS

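### Expected Benefits says symptom monitoring lets the study direct patients to care if swelling persists to six weeks after dose 2, but no visible survey contact is timed to observe it

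*Combined protocol and SAP*

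**What the plan says.** Under Expected Benefits, the protocol says that monitoring symptoms will enable the team to "direct patients to seek medical care in the event lymph node swelling symptoms persists to six weeks after the second dose". The next sentence describes the imaging standard on a different clock: for clinical concern lasting six or more "weeks after the final vaccine dose, axillary ultrasound is recommended per current MGH Breast Imaging standard of care".

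The contacts are set out in Research Design and Methods:

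- Participants still awaiting a second dose give its expected date and are "told that the invitation will be resent on that date via Patient Gateway for them to fill out a second survey on that dose".
- For the rest: "For participants who have had all doses of their respective vaccines, their participation is complete after responding to a survey about all applicable doses".
- For non-responders to the invitation: "A follow up phone call may be made if we do not hear back in 2 weeks". Resends at 72 hours and seven days are described as past practice.
- For consented participants who experienced swelling, the team will "provide them with contact information if they would like to schedule arm measurements before and/or after receiving the booster vaccination". Also: "We will resend an updated letter to participants who reported lymph node swelling after any of the three doses". Neither mailing is given a date relative to a dose.
- Optional arm measurements are offered 1-2 weeks before the booster, then at 7-14 days, 4-6 weeks and 3 months after it, with a two-week tolerance.

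Monitoring and Quality Assurance has the REDCap data reviewed every 8 weeks, for accuracy and completeness. On timing of the symptom, the background section on the vaccine and lymphedema risk says that lymphadenopathy after the Pfizer vaccine arose "within 2-4 days of vaccination and lasted for a mean of 10 days". It gives the same 2-4 day onset for Moderna, with a median duration of 1-2 days.

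**The concern.** The sentence presents direction to care as a consequence of monitoring. It stands in a form whose opening instructions say it is used to assess the risk-benefit ratio. A reader on the ethics committee would reasonably assume that some contact takes place at or near the named time point. If none does, persistence is seen only when a participant who is still swollen happens to answer, or to be seen, late enough. The background section says this swelling mimics nodal spread of breast cancer, so a statement about directing patients to care should match the procedures.

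There is a smaller consequence for the analysis. Statistical Methods says that the median duration of side effects was analysed for each mRNA dose, but not how an answer given while a side effect was still present was handled.

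**Working it through.** The plan gives no figure to reproduce here. The check is to list every timed contact and compare it with six weeks after dose 2, which is 6 × 7 = day 42.

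Assumption: the re-sent invitation goes out on the actual dose date, and the non-response prompts are counted from it.

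| Contact | Day after dose 2 | Short of day 42 by |
|---|---|---|
| Dose-2 survey invitation | 0 | 42 days |
| Resend at 72 hours (past practice) | 3 | 39 days |
| Resend at seven days (past practice) | 7 | 35 days |
| Possible phone call for non-response | 14 | 28 days |

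The invitation on day 0 precedes the cited onset by 2-4 days. None of these contacts reaches day 42.

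The booster arm measurements need separate treatment because they count from the booster. Nominal days are 7-14, 28-42 and about 91. If the two-week tolerance applies to every visit (assumed), the windows become:

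- first visit: 7 − 14 = −7 to 14 + 14 = 28
- second visit: 28 − 14 = 14 to 42 + 14 = 56
- third visit: 91 − 14 = 77 to 91 + 14 = 105

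The second visit can fall on day 42 after the booster and the third falls beyond it. They are optional, are not counted from dose 2, and are described as arm measurements.

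The remaining contacts are not timed to any dose:

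- The mailings to those with swelling are undated, and the first is described as offering arm measurements.
- Symptom screening follows oncology visits.
- The booster and prior-infection surveys go out on their own calendars.
- Adverse events are reviewed as they occur, but the text does not say whether a survey answer reporting swelling counts as one.
- The 8-weekly review is a data-quality check, with no visible rule linking a swelling answer to a referral.

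The two clocks in Expected Benefits coincide for someone whose final dose is the second. They differ for a one-dose vaccine and after a booster, and the study includes both.

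**The case against.** The strongest reply is that the record is incomplete. The surveys, letters, phone scripts, fact sheet and information sheet are attachments, and a figure is missing directly after the description of participation. An item on ongoing swelling, advice to seek care or a referral route could sit in any of them. This stands. It limits the point to the visible text and makes checking the attachments the first step.

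A second reply is that the sentence says only what the study will be able to do, in a section on benefits next to a remark on patient education, in an observational study of minimal risk. That is fair as to weight. It does not remove the mismatch, because the ability is attributed to monitoring and the visible monitoring has no contact at that point.

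Third, many participants may answer well after dose 2 and could then report lasting swelling. True, but that is incidental and not scheduled.

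Some stronger readings are tempting, and the documents do not support them:

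- A reader might infer that nothing in the plan reaches six weeks after any dose. The booster visits can.
- A reader might infer that persistent swelling was missed, or that participants were misled. No response times or counts are given, and the consent wording reproduced in Consent Procedures does not mention monitoring.
- A reader might infer that the analysed median durations are biased by a known amount. That would need response times and survey wording, neither of which is shown.
- A reader might call the two clocks a contradiction. They govern different actions; the text simply does not relate them.

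**Conclusion.** The point holds for dose 2 and for the visible text. The number of survey contacts timed to observe swelling six weeks after the second dose is zero, and the latest timed prompt falls 28 days short under the dose-date assumption above. The booster arm measurements are the only post-dose schedule and do not fill this gap. How many participants had swelling that lasted so long cannot be derived from the documents, so no count is claimed.

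The matter is minor: one benefit statement that the described procedures do not secure, for a symptom the protocol itself calls worrisome. The handling of ongoing durations is a secondary point with no magnitude attached.

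**What to change.** First, check the attachments and the missing figure for advice or a referral route. If one exists, cite it in Expected Benefits.

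Second, the investigator should reconcile the second-dose and final-dose clocks in that section. This review takes no view on which applies.

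Then one of two steps:

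- If collection is closed, as the past tense of Statistical Methods and the cited publication suggest, correct the monitoring statement to describe what was done. The cost is one sentence.
- If collection is open, add one short automatic REDCap follow-up for participants who report swelling, asking whether it is still present. Time it to the reconciled point and name the existing staff who read it. The cost is set-up, some staff time and a small participant burden. As an illustration, at the planned minimum of 989 participants, and assuming the Moderna rates quoted in the background apply to the whole cohort, this means 989 × 0.116 ≈ 115 to 989 × 0.160 ≈ 158 extra surveys per dose.

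In either case, if any durations were still running at response, treat them as right-censored, estimate the median by Kaplan-Meier, and show their number beside each median. The cost is one extra table column.

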This is a prospective, longitudinal observational cohort study incorporating patient-reported surveys before and/or after vaccine receipt. Female patients who are ≥ 18 years of age and have a history of breast cancer will be eligible. For the MGH site, patients must have received some breast cancer treatment at MGH or its affiliates and received perometry measurements to measure arm volume to be eligible for this study. Per our MGH lymphedema screening records, there are a minimum of 4,947 patients who will qualify for this study. Based on an anticipated survey response of 20%, we anticipate minimal accrual at MGH to be approximately 989 patients.

Briefly describe study procedures. Include any local site restrictions, for example, “Subjects enrolled at Partners will not participate in the pharmacokinetic portion of the study.” Describe study endpoints.

REDCap was used to develop surveys to be sent electronically to patients. We will use the surveys to elicit patient choices around receiving/not receiving the vaccine, injection site of choice and side effects. Complete versions of all survey involved in this study have been attached to this application, but not all questions will be relevant to each patient. Therefore, branching logic is built into our REDCap database to ensure patients only

have to answer the questions that are relevant to them. For example, a patient who receives a COVID-19 vaccine that only has one dose will not need to fill out symptoms information for their second dose as it is not applicable to them.

For all eligible patients from MGH who use MGB Patient Gateway, they will be sent a recruitment letter via MGB Patient Gateway with a REDCap survey link embedded. We have been working with the Partners eCare team to build this recruitment report.

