Upon completion of the survey study, we may apply for secondary use of data from our Screening Program to analyze perometry and clinicopathological data for participants who have responded to surveys regarding their COVID-19 vaccinations and who are established participants in our MGH Breast Cancer-Related Lymphedema Screening Program (2008P000540 and 1999P009256). We have applied for and been granted secondary use under Insight number 2021P003414. This program routinely screens patients starting at pre-operative baseline, throughout and beyond treatment at their oncology follow-up visits. Screening consists of perometry measurements, a valid and reliable measure of arm volume used for lymphedema screening[29], as well as a patient-reported outcome measure, the Symptoms Experience Index (SEI), a validated measure of symptoms after breast cancer surgery. Analysis of this data will inform BCRL risk after COVID-19 vaccination versus that from our historical control data.

For studies involving treatment or diagnosis, provide information about standard of care at Partners (e.g., BWH, MGH) and indicate how the study procedures differ from standard care. Provide information on available alternative treatments, procedures, or methods of diagnosis.

Not applicable: this study does not involve treatment or diagnosis.

Describe how risks to subjects are minimized, for example, by using procedures which are consistent with sound research design and which do not unnecessarily expose subjects to risk or by using procedures already being performed on the subject for diagnostic or treatment purposes.

The surveys sent, the main research components of this study, do not present risk to patients. We will protect patients by inviting the majority of the study participants through secure Patient Gateway contact. All surveys will be completed in REDCap and all survey responses will be stored in our secure REDCap database. All patients who are offered to participate in this study are already familiar with the MGH Lymphedema Research Program.

Describe explicitly the methods for ensuring the safety of subjects. Provide objective criteria for removing a subject from the study, for example, objective criteria for worsening disease/lack of improvement and/or unacceptable adverse events. The inclusion of objective drop criteria is especially important in studies designed with placebo control groups.

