clinical service and will be distributed to any patients in the Breast Cancer Center, regardless of their participation in research.

For guidance, refer to the following Partners policy:

Obtaining and Documenting Informed Consent of Subjects who do not Speak English
<https://www.partners.org/Assets/Documents/Medical-Research/ClinicalResearch/Non-English-Speaking-Subjects.pdf>

RECRUITMENT PROCEDURES

Explain in detail the specific methodology that will be used to recruit subjects. Specifically address how, when, where and by whom subjects will be identified and approached about participation. Include any specific recruitment methods used to enhance recruitment of women and minorities.

There are multiple recruitment methods for this study:

- The majority of patients will be accrued via recruitment letter sent through MGB Patient Gateway. We will send this letter to all MGH patients who are eligible (≥ 18 , female, treated for breast cancer at MGH, have been measured with perometry for BCRL) and are in our database (1999P009256/2008P000540). For patients who are okay with receiving research opportunities, the original letter directly from our study team will be sent to them. For all patients who are not enrolled at the time of the initial survey invitations, but become eligible, they may be accrued either by provider referral or when they are in clinic seeing our Clinical Research Coordinators for a perometry measurement. This group of patients includes those diagnosed with breast cancer after the surveys have been sent out or those who have received perometry measurements for clinical purposes. CRCs will mention the study during a regular screening visit and send the email to the patient if they are interested or give them a flyer (attached) so a patient can decide if they would like to join after the visit is over and they have time to think about it. The same could happen if a provider mentions the study to a patient who then approaches our team about the study.

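### Women who enter through clinic perometry visits or provider referral are pooled with the mailed cohort, so the node-swelling rate set against the general population could be biased upward by an unknown amount

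*Combined protocol and SAP*

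**What the plan says.** Research Design and Methods requires MGH patients to have "received perometry measurements to measure arm volume to be eligible for this study". It states that "there are a minimum of 4,947 patients who will qualify for this study" and, at an anticipated 20% response, expects about 989 women.

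Recruitment Procedures describes the main route: "The majority of patients will be accrued via recruitment letter sent through MGB Patient Gateway". For women not enrolled at the initial invitations who become eligible later, it adds that "they may be accrued either by provider referral or when they are in clinic seeing our Clinical Research Coordinators for a perometry measurement". That group covers women diagnosed after the surveys went out and "those who have received perometry measurements for clinical purposes". The reason for those clinical measurements is not given.

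Research Design and Methods allows surveys before and/or after vaccination. A woman who has had all her doses finishes with a survey covering all of them. No rule places the qualifying measurement or the referral before vaccination.

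Statistical Methods reports side-effect frequencies for each mRNA dose and fits one model per side effect across all doses. The covariates are age, BMI, surgery type, axillary surgery, radiation and chemotherapy. Accrual route is not among them, and no analysis by route is planned. Hypothesis 2 in Specific Aims expects axillary node swelling at the general-population rate.

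**The concern.** The mailed list was drawn from an existing database, so being on it does not depend on what happened after a woman's vaccination. The later routes lack that protection. A woman who noticed swelling, raised it with a provider and was then referred or measured could enter because of the symptom. A similar woman without symptoms would have had no such prompt. Her survey would then report the swelling retrospectively.

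This matters most for an absolute rate judged against an outside figure. In a comparison between groups within the study, some of this selection might cancel; against the general population it does not. Weighting responders back to the invited list would not repair it either, because these women were not on that list.

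**Working it through.** **The plan's own figure.** 4,947 × 0.20 = 989.4, which reproduces the stated 989. The documents give no power calculation or target precision to check.

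**Inputs from the documents**
- N = 989, taken here as the size of the analysed sample.
- Reference axillary swelling rates from Background and Significance (Moderna): 11.6% after dose 1 and 16.0% after dose 2. They stand in for the mailed-cohort rate p.
- The letter is the majority route, so the late-entrant share is below 50%.

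**Assumed inputs (not in the documents)**
- f, the share of women entering by clinic visit or referral.
- RR, their node-swelling rate divided by that of mailed women.

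**Pooled rate:** p × [1 + f × (RR − 1)]. For example, 0.160 × [1 + 0.10 × (2 − 1)] = 0.176.

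| f | RR | 11.6% is observed as | 16.0% is observed as |
|---|---|---|---|
| any | 1 | 11.6% | 16.0% |
| 5% | 2 | 12.2% | 16.8% |
| 10% | 2 | 12.8% | 17.6% |
| 10% | 3 | 13.9% | 19.2% |
| 20% | 2 | 13.9% | 19.2% |
| 20% | 3 | 16.2% | 22.4% |

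**Sampling error for scale:** the 95% half-width is 1.96 × √[p(1 − p)/989].
- p = 0.116: 1.96 × √(0.1025/989) = 0.020, or 2.0 points.
- p = 0.160: 1.96 × √(0.1344/989) = 0.023, or 2.3 points.

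**Share at which bias equals the half-width:** f = half-width / [p × (RR − 1)].
- RR = 2: 0.0200/0.116 = 17.2%; 0.0228/0.160 = 14.3%.
- RR = 3: 0.0200/0.232 = 8.6%; 0.0228/0.320 = 7.1%.

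A smaller denominator for a given dose would widen the half-width and raise these thresholds; a larger accrual would lower them.

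**The case against.** The strongest reply is that the documents describe routine entry. The mailing goes to women in the database of the two screening protocols, so perometry for clinical purposes most naturally means perometry done outside those protocols, not perometry prompted by a symptom. The text then says "CRCs will mention the study during a regular screening visit", and of the screening programme Research Design and Methods says "This program routinely screens patients starting at pre-operative baseline". A reader might infer that swelling itself is the way into the study. No section says so, and this wording points the other way.

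The outcome also fits the entry criterion poorly. Perometry measures arm volume, whereas Hypothesis 2 concerns axillary nodes. For concern that persists at least six weeks after the final dose, Expected Benefits refers to axillary ultrasound, not perometry. Background and Significance gives a short course for the swelling: a median of 1–2 days for one vaccine and a mean of 10 days for the other. It is therefore an unlikely trigger for a first arm-volume visit. Research Design and Methods does offer arm measurements to women who report swelling, but those women are already enrolled, so this does not show how late entrants arrived.

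These arguments lower the likely size of the effect without closing the route. Provider referral needs no swelling at the time of the visit, the survey is retrospective, and entry after symptoms is allowed. With route absent from the analysis, the reported results could not show whether the effect is trivial.

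**Conclusion.** The concern holds in a limited form. Entry that depends on swelling is possible, is not ruled out, and would push the descriptive node-swelling frequency upward. Its size cannot be derived from the documents, because f and RR are both unknown. There is no bias at RR = 1. With few late entrants or a modest RR it stays within sampling error, and it passes that level only beyond the shares worked out above. Those thresholds rest on N = 989 and on the Moderna reference rates standing in for the mailed cohort.

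A reader might also infer that lymphedema rates are inflated. The documents do not support that. Statistical Methods plans no lymphedema rate. The comparison described by "Analysis of this data will inform BCRL risk after COVID-19 vaccination versus that from our historical control data" belongs to a separate secondary-use analysis, limited to established participants in the screening programme. Women measured only for clinical purposes may well fall outside it.

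**What to change.** 1. Record accrual route for every woman: mailed letter, clinic visit or provider referral. Assign it by whether she was on the list at the initial invitations, not by where she completed the survey, since women also in the CANVAX study may complete it during a visit.
2. Record the reason for the qualifying perometry where it is available. The consent fact sheet already covers review of medical records.
3. Use the node-swelling frequency per dose in the mailed list as the estimate compared with the general-population rate.
4. Show the same frequency with clinic and referral entrants added. Keep newly diagnosed women who came through routine baseline screening as a separate, identifiable group.

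A rule that the qualifying perometry must precede the first dose is not advisable. It would also remove women diagnosed and routinely measured after vaccination, whom Equitable Selection of Subjects deliberately includes.

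The cost is one route variable, one sentence defining the analysis set and one extra table. A few women leave the main rate estimate but stay in the descriptive tables and the regression models. As the Statistical Methods describe an analysis already carried out, this can be done as a supplementary analysis of existing data.
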